### 8.1.2.1 Monitoring for Corticosteroid Treatment

For subjects receiving concomitant corticosteroids, the Treating Physician should continue the monitoring and management of corticosteroid treatment at every study visit according to current standard of care and as recommended by the protocol. It is anticipated that subjects in the study were previously on corticosteroids that have been reduced to prednisolone equivalent 20 mg/day or less at least 1 month before Baseline. Further dose reduction (taper) must be started at Week 17 if clinically relevant improvement (see [Section 3.1](#)) has been achieved. Subjects with clinical worsening in Study Period 1 (eg, subject meets DOW criteria) will be eligible for oral corticosteroid rescue treatment of up to prednisolone equivalent 1 mg/kg daily for up to 5 days to be given at the discretion of the Treating Physician. Corticosteroids are known to be associated with a variety of side effects in a dose- and duration-of-treatment-dependent manner [[Oray et al, 2016](#)]. Please refer to [Section 5.3.1](#) for more information on rescue treatment. Reporting of AEs related to corticosteroid treatment should be handled according to [Section 9.2](#).

### 8.1.2.2 Monitoring for Thromboembolic Events (TEEs)

To reduce the risk of potential TEEs, this study excludes specific patient groups ([Section 4.1.2](#), exclusion criterion 6 items pertaining to TEE risk). Nevertheless, TEE risk will be continuously monitored during the study.

---

The Treating Physician will assess the subject for the suspicion of a TEE per standard of care at every study visit during all Study Periods.

If there is suspicion of DVT or PE during Study Periods 1 or 2, the Wells' Criteria for DVT ([Table 9](#)) or Wells' Criteria for PE ([Table 10](#)) will be assessed and entered in the eCRF [[Modi et al, 2016](#); [Wells' Criteria for DVT](#); [Doherty, 2017](#); [Wells' Criteria for Pulmonary Embolism](#)].

A score of  $> 1$  on the Wells' Criteria for DVT requires diagnostic imaging (lower extremity ultrasound) to rule out DVT. A score of  $> 1$  on the Wells' Criteria for PE requires additional imaging, (eg, computerized tomography scan, ventilation/perfusion scan, pulmonary angiography, or other modalities) be performed as per the site's standard of care.

When a diagnosis of DVT or PE is confirmed, IMP treatment must be discontinued; however, the subject may continue in the study for other study assessments up until Week 53. During Study Period 3, there will be no formal assessment of Wells' Criteria. TEEs will be monitored as part of standard assessment for AEs at each monthly site visit. If a TEE occurs during participation in Study Period 3, the subject must be discontinued from the study.

**Table 9****Wells' Criteria Scoring for Suspicion of DVT**

Assessment	Score
Active cancer (Treatment or palliation within 6 months) A	+1
Bedridden recently > 3 days or major surgery within 12 weeks A	+1
Calf swelling > 3 cm compared to the other leg (Measured 10 cm below tibial tuberosity)	+1
Collateral (nonvaricose) superficial veins present	+1
Entire leg swollen	+1
Localized tenderness along the deep venous system	+1
Pitting edema, confined to symptomatic leg	+1
Paralysis, paresis, or recent plaster immobilization of the lower extremity	+1
Previously documented DVT A	+1
Alternative diagnosis to DVT as likely or more likely	-2
Total Score	

DVT = deep vein thrombosis.

A Exclusion Criterion (see [Section 4.1.2](#))**Table 10****Wells' Criteria Scoring for Suspicion of PE**

Assessment	Score
Clinical signs and symptoms of DVT	+3
PE is #1 diagnosis OR equally likely	+3
Heart rate > 100 bpm	+1.5
Immobilization at least 3 days OR surgery in the previous 4 weeks A	+1.5
Previous, objectively diagnosed PE or DVT A	+1.5
Hemoptysis	+1
Malignancy with treatment within 6 months or palliative A	+1
Total Score	

DVT = deep vein thrombosis; PE = pulmonary embolism.

A Exclusion Criterion (see [Section 4.1.2](#))

All TEEs, including but not limited to DVT and PE, will be classified as AESIs (see [Sections 9.1.3](#) and [9.6.2](#)). Follow-up monitoring and treatment (eg, anticoagulation) will be performed according to the site's standard of care using established guidelines (eg, American Society of Hematology 2018).

### 8.1.2.3 Monitoring for Hemolysis

For determination of hemolysis, an assessment of clinical signs of hemolysis will be performed at Week 2 and Week 5 and compared to Baseline. In combination with laboratory results confirmed or suspected hemolysis cases will be defined as follows:

#### ***Confirmed hemolysis:***

Subjects fulfilling criterion A and at least 2 of criteria B, where 1 of the minor criteria must be direct antiglobulin test (DAT) positive after infusion and within 28 days of the first IMP infusion, will be considered to have “confirmed hemolysis.” Confirmed hemolysis will be reported as an AE.

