Waist circumference	X								X								X			
IMP assignment E,F	X		X	X	X	X	X	X	X	X	X	X	X	X	X	X G	X H			
Vital signs H	X		X	X	X	X	X	X	X	X	X	X	X	X	X	X	X			
Safety assessments I	X		X	X	X	X	X	X	X	X	X	X	X	X	X	X	X			
Laboratory collections:																				
Urine hCG pregnancy test J	X			X	X	X	X	X	X	X	X	X	X	X	X	X	X			
Serum exploratory biomarkers E,K	X			X	X		X	X	X			X				X	X			
DNA exploratory biomarkers L	X																			
RNA exploratory biomarkers E	X			X					X								X			
Hematology M	X		X	X	X		X		X		X			X		X	X			
HbA1c	X								X								X			
Muscle enzymes N	X			X	X	X	X	X	X	X	X	X	X	X	X	X	X			
Additional labs for hemolysis criteria O	X		X	X																
Other biochemistry P	X				X		X		X		X			X		X	X			

Study Year	Year 1 A																	UNS	
Study Period	Study Period 1 B										Study Period 2 B								
Study Week	Base -line	W1	W2 ±3d	W5 ±3d	W9 ±3d	W13 ±3d	W17 ±3d	W21 ±3d	W25 EOP1 ±3d	W29 ±3d	W33 ±3d	W37 ±3d	W41 ±3d	W45 ±3d	W49 ±3d	W53 C ±3d	W56 EOP2 ±3d		
Assessments																			
Coagulation Q	X		X	X	X	X	X	X	X	X	X	X	X	X	X	X		X	
Serum IgG levels E	X		X	X	X		X	X	X			X			X	X		X	
Rich PK sampling E												X K							
ANA, MSA, and MAA E,R									X							X			
Virology retention sample E,S	X															X			
IMP SC infusion E,T,U		X	X	X-----X													X G	X X	
Subject SC Infusion Diary review E		X	X	X	X	X	X	X	X	X	X	X	X	X	X	X		X	
AEs	X																X	X	
Concomitant therapies		X															X	X	
Change to physiotherapy V	X		X	X	X	X	X	X	X	X	X	X	X	X	X	X		X	
DOW Y			X	X	X	X	X	X	X							X		X	
Assess for clinically relevant improvement Z	X						X	X	X	X	X	X	X	X	X			X	
Individual CSMs AA	X		X	X	X	X	X	X	X	X	X	X	X	X	X	X		X	
CDASI	X		X	X	X	X	X	X	X	X	X	X	X	X	X	X		X	
5-D Itch Score	X			X		X			X		X		X				X		
Timed Up and Go	X			X		X			X		X		X				X		
EQ-5D-5L, WPAI-GH, and TSQM-9 E,BB	X					X			X		X		X			X			
Review eligibility for open-label Study Period 3																X			

Study Year	Year 1 A																UNS
Study Period	Study Period 1 B										Study Period 2 B						UNS

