- Additional laboratory collection for Week 37 is located in [Schedule of Assessments for Rich Pharmacokinetic Sampling](#).
- Optional DNA blood samples for exploratory biomarkers.
- Hematology: hemoglobin, hematocrit, platelets, erythrocytes, leukocytes with differential counts (neutrophils, basophils, eosinophils, lymphocytes, monocytes).
- Muscle enzymes: CK, LDH, AST, ALT, aldolase.

- O. Hemolysis: DAT, total bilirubin, direct bilirubin, indirect bilirubin, haptoglobin, reticulocytes, and peripheral blood smear to check for spherocytosis. Peripheral blood smear will be performed at Week 2 and Week 5 only.
- P. Other biochemistry: sodium, potassium, chloride, bicarbonate, BUN, glucose, GGT, alkaline phosphatase, creatinine.
- Q. Coagulation: D-dimer complex.
- R. MSA and MAA: anti-Jo-1, anti-PL-7, anti-PL-12, anti-EJ, anti-OJ, anti-SRP, anti-Mi-2, anti-p155/140, anti-TIF-1 $\gamma$ , anti-MDA5, anti-NXP-2, anti-PM/Scl, anti-Ro-SSA, anti-Ku, anti-U1 RNP, anti-U3 RNP, anti-HMGCR, anti-SAE-1Ab.
- S. Retention samples at Baseline and Week 53/end of study participation. A virology retention sample should be obtained for all subjects who discontinue at any time during the study.
- T. IMP SC infusions at Week 1 and Week 2 are to be administered only after the visit-specific assessments (except SC infusion diary review) are completed.
- U. Training and supervised IMP SC infusions at the site on Week 1 and Week 2. If additional infusion training at the site is requested by the subject for Week 3 and/or Week 4, no other UNS Visit assessments are required to be performed. Week 3 and Week 4 additional infusion training will be documented in the eCRF. After training is completed, IMP will not be administered during subsequent study visits. For the remainder of their participation in the study, subjects will self-administer IMP at home.
- V. Physiotherapy regimen may be modified starting at Week 17 if clinically relevant improvement is achieved.
- W. Only if subject discontinues IMP treatment before Week 25.
- X. IMP will only be administered at the site for unscheduled visits which occur at Week 3 or Week 4.
- Y. See [Section 5.3.1](#) for DOW criteria and corticosteroid rescue details (Week 9 to Week 25). DOW assessment at UNS Visit only if before Week 25.
- Z.  $\geq 2$  cm improvement from Baseline on 10-cm Physician Global Disease Activity VAS.

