Other biochemistry	
 
Alkaline phosphatase
 
Chloride
 
Glucose
 
Bicarbonate
 
GGT
 
Potassium
 
BUN
 
Sodium
 
Creatinine
 
		

Assessment	Description
Coagulation	• D-dimer
Virus serology	Blood samples are to be tested for HBsAg, HCV antibodies, and HIV-1, HIV-2 antibodies

ABO = blood group type A, type B, type AB, or type O; ALT = alanine aminotransferase; AST = aspartate aminotransferase; BUN = blood urea nitrogen; CK = creatine kinase; DAT = direct antiglobulin test; DM = dermatomyositis; ECG = electrocardiogram; GGT = gamma-glutamyl transferase; HbA1c = glycated hemoglobin; HBsAg = hepatitis B virus surface antigen; hCG = human chorionic gonadotropin; HCV = hepatitis C virus; HIV = human immunodeficiency virus; LDH = lactate dehydrogenase; Rh = Rhesus.

A Serum/urine pregnancy test is to be completed for all females of reproductive potential. A female of reproductive potential is defined as a premenopausal female capable of becoming pregnant. This includes women on oral, injectable, or mechanical contraception and women whose partners have been vasectomized or have received or are utilizing mechanical contraceptive devices.

B Known deficiencies in proteins C, protein S, and antithrombin-III levels and presence of lupus anticoagulant/cardiolipin antibodies (antiphospholipid antibodies) and/or the 2 gene mutations (Prothrombin G20210A and Factor V Leiden) will exclude a subject from the study ([Section 4.1.2](#), Exclusion Criterion 6).

C Peripheral blood smear will only be analyzed for a drop in hemoglobin from the previous study visit  $\geq 1$  g/dL.

Results of laboratory tests should be signed and dated in a timely manner and retained at the study site as source data. Refer to [Section 9](#) for information on how AEs based on laboratory tests should be assessed and reported.

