#### ***Suspected hemolysis:***

Subjects fulfilling criterion A and at least 1 of criteria B will be considered to have “suspected hemolysis.”

- Criterion A
  - Drop in hemoglobin of > 1 g/dL since the time of first administration of IMP without clinical evidence of blood loss from gastrointestinal bleeding, menorrhagia, hemoptysis, major hematoma, or injury and not explained by repeated phlebotomy
- Criteria B
  - Presence of minor criteria documented since the time of first administration of IMP, consisting of:
    - DAT positive
    - Haptoglobin < lower limit of normal
    - LDH > ULN
    - Total or indirect (unconjugated) bilirubin > ULN or jaundiced
    - Hemoglobinuria or red/dark urine
    - Hemoglobinemia
    - Spherocytosis
    - Hepatosplenomegaly

If AE of hemolysis is reported, it must be graded by the investigator:

- Grade 1 – Laboratory evidence of hemolysis only (eg, DAT positive, schistocytes, decreased haptoglobin)
- Grade 2 – Clinical evidence of hemolysis and  $\geq 2$  g/dL decrease in hemoglobin
- Grade 3 – Transfusion or medical intervention indicated (eg, steroids)
- Grade 4 – Life-threatening consequences; urgent intervention indicated
- Grade 5 – Death

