**Table 14** **Time Windows for Assessments**

Visit/Procedure	Time window (relative to scheduled visit/procedure)
Screening	Up to 2 months before Baseline
Week 2 and all subsequent study visits in Study Period 1 and Study Period 2	$\pm$ 3 days
Monthly study visits in Study Period 3	$\pm$ 7 days
Physical examination, to include Physician Global Damage Assessment only at Screening	Before first SC infusion on Week 1 A
Vital signs, including body weight	Before first SC infusion on Week 1 and Week 2 A
Urine collection for pregnancy test B	Before first SC infusion on Week 1 A
Blood collection for laboratory tests	Before first SC infusion on Week 1 and Week 2 A
Blood collection for rich PK (serum IgG and exploratory biomarkers)	Week 37, trough sample collection at study visit Week 37, $24 \pm 3$ h relative to the start of first infusion Week 37, $48 \pm 3$ h relative to the start of first infusion Week 37, $72 \pm 3$ h relative to the start of first infusion Week 37, $120 \pm 3$ h relative to the start of first infusion Week 37, $168 \pm 3$ h relative to the start of first infusion
Subject SC Infusion Diary review	At the end of SC infusions on Week 1 and Week 2 A
Adverse event documentation	Before first SC infusion on Week 1 and Week 2 A
Safety assessment documentation	Before first SC infusion on Week 1 and Week 2 A

Visit/Procedure	Time window (relative to scheduled visit/procedure)
Concomitant therapy documentation	Before first SC infusion on Week 1 and Week 2 A
Physiotherapy documentation	Before first SC infusion on Week 1 and Week 2 A
Efficacy assessments	Before first SC infusion on Week 1 and Week 2 A

h = hour; IgG = immunoglobulin G; PK = pharmacokinetic; SC = subcutaneous.

A For all other study visits, SC infusions are not performed at the study visit.

B Urine pregnancy test is to be completed for all females of reproductive potential.

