### **Week 1**

- Document AEs
- Document concomitant therapies
- Training and supervision of first IMP SC infusion
- Supervision of subject SC Infusion Diary entry

### 8.5.3.2 Week 2

The following procedures will be conducted at 1 week  $\pm$  3 days after the first SC infusion of IMP:

- Body weight
- IMP assignment
- Vital signs
- Safety assessments
- Collection of blood samples to assess the following:
  - Hematology with peripheral blood smear
  - Hemolysis
  - Coagulation
  - Serum IgG
- Training and supervision of IMP SC infusion for Week 2
- Supervision of subject SC Infusion Diary entry
- Document AEs
- Document concomitant therapies
- Document any change to physiotherapy since the previous study visit

Starting with Week 3, the subject will adjust their first dosing day so that no SC infusions occur on the day of a study visit. Site instruction for this transition should be provided.

### 8.5.3.3 Week 5

The following procedures will be conducted at 4 weeks  $\pm$  3 days after the first SC infusion of IMP:

- Body weight
- IMP assignment
- Vital signs
- Safety assessments
- Collection of urine sample for hCG pregnancy test, if applicable

- Collection of blood samples for exploratory biomarkers (serum and RNA analyses)
- Collection of blood samples to assess the following:
  - Hematology with peripheral blood smear
  - Muscle enzymes
  - Hemolysis
  - Coagulation
  - Serum IgG
- Subject SC Infusion Diary review
- Document AEs
- Document concomitant therapies
- Document any change to physiotherapy since the previous study visit
- DOW assessment
- Individual CSMs
- CDASI

#### 8.5.3.4 Week 9

The following procedures will be conducted at 8 weeks  $\pm$  3 days after the first SC infusion of IMP:

- Body weight
- IMP assignment
- Vital signs
- Safety assessments
- Collection of urine sample for hCG pregnancy test, if applicable
- Collection of blood samples for exploratory biomarkers (serum analysis)
- Collection of blood samples to assess the following:
  - Hematology
  - Muscle enzymes
  - Other biochemistry

- Coagulation
- Serum IgG
- Subject SC Infusion Diary review
- Document AEs
- Document concomitant therapies
- Document any change to physiotherapy since the previous study visit
- DOW assessment
- Individual CSMs
- CDASI
- 5-D Itch Score
- Timed Up and Go

### 8.5.3.5 Week 13

The following procedures will be conducted at 12 weeks  $\pm$  3 days after the first infusion of IMP:

- Body weight
- IMP assignment
- Vital signs

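### A first positive DAT drawn on days 29 to 31, inside the permitted Week 5 window, cannot count towards confirmed hemolysis because the case definition stops at 28 days

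*Protocol*

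**What the plan says.** **Case definition.** Under Protocol 8.1.2.3, confirmed hemolysis needs Criterion A (a hemoglobin drop of more than 1 g/dL) and at least two minor criteria. One of the two has to be "direct antiglobulin test (DAT) positive after infusion and within 28 days of the first IMP infusion". SAP 11.6.4 repeats this in the same words. Neither document adds an allowance for visit windows. Suspected hemolysis needs Criterion A and any one minor criterion, with no 28-day limit. The instruction to report hemolysis as an AE is attached to the confirmed category only.

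**Sampling.** Protocol 8.1.2.3 states that "an assessment of clinical signs of hemolysis will be performed at Week 2 and Week 5 and compared to Baseline". In Table 2 of the protocol, the row "Additional labs for hemolysis criteria" is marked at Baseline, Week 2 and Week 5 only. Note O to that table defines the panel: "Hemolysis: DAT, total bilirubin, direct bilirubin, indirect bilirubin, haptoglobin, reticulocytes, and peripheral blood smear to check for spherocytosis". The panel is not in the list of laboratory tests for unscheduled visits (Protocol 8.5.4.9).

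**Visit timing.** Protocol 8.5.3.3 places Week 5 at "4 weeks $\pm$ 3 days after the first SC infusion of IMP". Table 14 gives the same 3-day tolerance for "Week 2 and all subsequent study visits in Study Period 1 and Study Period 2".

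**Smear.** Table 8, note C, says "Peripheral blood smear will only be analyzed for a drop in hemoglobin from the previous study visit" of at least 1 g/dL. Criterion A measures the drop from a different starting point: "since the time of first administration of IMP without clinical evidence of blood loss".

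**The concern.** The last scheduled DAT may be drawn up to three days after the limit that decides whether it counts. Two subjects with the same hemoglobin drop, the same low haptoglobin and the same first positive DAT at Week 5 would be classed differently if one attended on day 27 and the other on day 30, although both visits comply with the protocol. The first is confirmed and must be reported as an AE. The second is suspected, and AE reporting is left to the investigator's judgement.

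The rule also sits awkwardly with SAP 8.2.7, which reports data by nominal visit and applies no visit windows. The same DAT result would be tabulated as Week 5 data but disregarded for case status because of its calendar day.

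The smear rule raises a smaller question of the same kind. Whether the smear is read depends on the change since the last visit, while the case definition depends on the change since the first dose.

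**Working it through.** The documents give no computed figure to reproduce. The check is date arithmetic on their stated rules.

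**Inputs**
- DAT limit: 28 days from the first infusion (Protocol 8.1.2.3, SAP 11.6.4).
- Week 5 visit: 4 weeks ± 3 days after the first infusion (Protocol 8.5.3.3, Table 14).
- Week 2 visit: 1 week ± 3 days after the first infusion (Protocol 8.5.3.2, Table 14).
- Study-day rule: date of interest minus date of first infusion, plus 1, so the first infusion is on Day 1 (SAP 8.2.2).

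**Step 1: permitted days.**
- Week 5: 4 × 7 = 28, and 28 ± 3 gives elapsed days 25, 26, 27, 28, 29, 30 and 31, which is 7 days.
- Week 2: 7 ± 3 gives elapsed days 4 to 10, all inside the limit.

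**Step 2: compare Week 5 with the limit.**

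| How 28 days is counted | Week 5 window | Meets the limit | Fails the limit | Share of days failing |
|---|---|---|---|---|
| Elapsed days since first infusion | 25–31 | 25–28 | 29, 30, 31 | 3/7 = 43% |
| SAP study days (elapsed + 1) | 26–32 | 26–28 | 29, 30, 31, 32 | 4/7 = 57% |

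On the second count, the nominal Week 5 date (28 elapsed days, Study Day 29) fails as well. Neither document says which count applies, and the nominal date lies exactly on the boundary.

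**Step 3: what the limit would have to be.** To include every compliant Week 5 draw, it would have to reach 28 + 3 = 31 elapsed days (Study Day 32), or be defined by the visit.

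**Step 4: who is affected.** All of the following must hold: Criterion A is met; at least one minor criterion other than DAT is met; the Week 2 DAT was not positive; and the Week 5 DAT is positive and drawn on elapsed days 29 to 31. The documents give no rate for any of these and no distribution of attendance within the window.

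**Step 5: smear.** Take a drop of 0.9 g/dL from Baseline to Week 2 and a further 0.9 g/dL from Week 2 to Week 5. Each step is below 1 g/dL, so note C does not call for the smear to be read. The total since first dose is 0.9 + 0.9 = 1.8 g/dL, which exceeds 1 g/dL and meets Criterion A. Spherocytosis is one of eight minor criteria, and confirmation needs DAT plus any one other. The unread smear therefore changes confirmed status only if spherocytosis would have been the sole second criterion.

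**The case against.** The strongest case on the other side is that little is lost.

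- **The case is still counted.** A late first positive meets the suspected definition. Protocol 10.4.3 summarizes suspected and confirmed hemolysis, and SAP 11.6.4 reports hemolysis findings descriptively. This stands.
- **AE capture has another route.** Protocol 9.1.1 requires laboratory findings that the investigator judges clinically significant to be recorded as AEs. The hemolysis grading starts at laboratory evidence alone, and the discontinuation list in Protocol 4.3.1 refers to Grade 3 hemolysis and not to the confirmed label. This also stands. What is missing is the automatic rule for a narrow group.
- **Extra samples are possible.** Protocol 8.1 and 8.2 allow more frequent assessments, and repeat or unscheduled blood samples for safety reasons. An unscheduled DAT is not barred, but nothing in the plan ensures one before the limit.
- **Weight.** Hemolysis carries no hypothesis test or stopping rule, and the definition is the same in both blinded arms. No bias between arms is shown.

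A reader might also infer more than the text supports. It would be wrong to say that on-time Week 5 positives in general cannot be confirmed: on the elapsed-day reading, draws on days 25 to 28 qualify, and a positive Week 2 DAT satisfies the condition whatever the Week 5 date. Nor do the documents name confirmed cases as the main hemolysis count or describe hemolysis as an established risk of the product. They show only that it is specifically monitored.

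**Conclusion.** The conflict holds in a limited form. Protocol 8.1.2.3 and SAP 11.6.4 set a 28-day limit that the permitted Week 5 window overruns by three days. A first positive DAT on elapsed days 29 to 31 therefore leaves the subject classed as suspected, whatever the other findings, and outside the automatic AE-reporting rule.

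The size is 3 of 7 permitted days if 28 days means elapsed days, and 4 of 7, including the nominal date, if it means SAP study days. It is tempting to read 43% or 57% as the share of Week 5 results or of subjects affected. That would require attendance spread evenly over the window, for which the documents give no support, and the affected group must also satisfy every condition in Step 4 of the working. Its size cannot be estimated.

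The consequence is a safety classification that depends on which compliant day the subject attended, not a loss of data. It merits correction because it changes a reported category and its AE rule and costs almost nothing to put right. The smear mismatch is real but secondary.

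**What to change.** Reconcile the DAT limit in Protocol 8.1.2.3 and SAP 11.6.4 with the Week 5 window in Protocol 8.5.3.3 and Table 14. One way is to define the DAT condition, in both the case definition and the SAP derivation, by the scheduled Week 2 or Week 5 sample including its visit window. If a day limit is kept, state whether it counts elapsed days or SAP study days, and whether the nominal Week 5 date is inside it. The documents do not show which side of the conflict was intended, so the sponsor should say so.

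Separately, reconcile Table 8, note C, with Criterion A, so that the reading of the smear and the case definition refer to the same starting hemoglobin, or explain why they differ.

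The cost is a phrase in each document. Tying the condition to the scheduled samples needs no added visit or blood draw, and for data already collected the classification can be derived again from recorded DAT results and dates. The downside is that the confirmed count may rise slightly, and a few more smears from samples already scheduled may have to be read.
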